8.3.2. Description of baseline variables

Baseline variables will include:

- Demographic characteristics
- Medical history
- Past and concomitant anti-thrombotic medications
- Clinical status at study entry
- Baseline lesion characteristics

8.3.3. Primary analysis

The study will have co-primary endpoints. The co-primary endpoints are minimum stent area (MSA) at the site of maximum calcification measured at the end of the index procedure and target lesion failure (TLF) defined as the composite of cardiac death, non-fatal myocardial infarction related to the target vessel, and unplanned ischemia-driven target lesion revascularization at one-year post-procedure. MSA is a numerical measurement in millimeters, measured at the independent imaging core laboratory. TLF is a binary endpoint (TLF or no TLF).

The primary analysis will be conducted on the FAS and will estimate the proportion of TLF at 1-year with corresponding exact two-sided 95% CI. Descriptive analyses for MSA will be performed.

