Primary Endpoints:	
The study will have co-primary endpoints:
 
 1. Minimum stent area (MSA) at the site of maximum calcification measured at the end of the index procedure 2. Target lesion failure (TLF) (cardiovascular death, non-fatal myocardial infarction (MI) related to the target vessel, unplanned ischemia-driven target lesion revascularization) at 1 year
Secondary Endpoints:	
 1. Individual components of TLF at 1 month and 1 year 2. Minimum stent area (MSA) at the end of the index procedure 3. Strategy success defined as: 
 a) Successful stent delivery b) $\geq 80\%$ stent expansion c) Complete stent apposition d) No edge dissection e) Full lesion coverage with $<50\%$ plaque burden at proximal and distal references f) TIMI 3 flow 4. Target vessel revascularization (TVR) 5. Target lesion revascularization (TLR) 6. Stent thrombosis 7. Stroke 8. Cardiovascular death

	9. Acute kidney injury 10. Major bleeding, categorized as class 3-5 according to the Bleeding Academic Research Consortium [BARC] 11. Procedure time 12. Fluoroscopy time 13. Radiation exposure (dose-area-product) 14. Cost effectiveness analysis
Sample size:	500 patients
Inclusion Criteria:	1. Documented myocardial ischaemia. 2. At least one moderate to severely calcified native coronary artery lesion confirmed by QCA and/or 60MHz HD IVUS, with the presence of significant calcium, $\geq 70\%$ diameter stenosis by visual estimation (in a reference vessel diameter of $\geq 2.5\text{mm}$ and $\leq 4.0\text{mm}$) and TIMI 3 flow at baseline that is suitable for PCI. a. Significant calcium at the target lesion site is defined as either: i. The presence of radiopacities involving both sides of the arterial wall $>10\text{mm}$ and involving the target lesion on angiography. or ii. The presence of $>270^\circ$ arc of superficial calcium on HD intravascular imaging with a length $>5\text{mm}$ or the presence of 360° arc of calcium on HD intravascular imaging. [1] 3. It is possible to cross the calcified lesion with a coronary guidewire. 4. Age ≥ 18 years. 5. Patient is willing and able to comply with the study procedures and follow-up.

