3.1. General

This study is an international, multi-centre, observational, single-arm study. A total of 500 patients will be enrolled at 25 centers in Europe.

Patients will be screened before coronary angiography, and patients with planned PCI for moderate to severely calcified native coronary artery lesion will be eligible.

All procedures will be performed by fully trained operators with at least 50 prior rotablation procedures and several years of interventional experience. [5] All procedures will be performed according to current guidelines and international standards using a biodegradable-polymer,

Everolimus-eluting stent. [8, 10] In all patients, HD 60 MHz HD IVUS imaging will be performed according to a study-specific algorithm (outlined in section 5.6.3) after 1. crossing the lesion with a coronary guidewire, 2. after lesion preparation, and 3. after stent implantation to ascertain an optimal procedural result.

Baseline characteristics, vital signs, concomitant diseases, cardiovascular risk factors, medication, routine laboratory analyses, ECG data, coronary angiography, and procedural data (coronary angiogram, HD IVUS images, procedural characteristics, and periprocedural complications), and follow-up data will be collected.

The co-primary end points are minimum stent area (MSA) at the site of maximum calcification at the end of the index procedure (as assessed by 60MHz HD IVUS imaging) and rates of target lesion failure (TLF), a composite of cardiovascular death, non-fatal myocardial infarction related to the target vessel, and unplanned ischemia-driven target lesion revascularization, at 1 year.

Coronary angiograms and HD IVUS images will be analyzed by an independent angiography and HD IVUS Core Lab. Follow-up will be performed at discharge, at 30 days, and at 1 year.

The study will be conducted in accordance with the investigation plan, the current version of the Declaration of Helsinki, and national legal and regulatory requirements. [2]

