3.3. Endpoints

3.3.1. Co-Primary Endpoint

1. Minimum stent area (MSA) at the site of maximum calcification at the end of the index procedure
2. Target lesion failure (TLF) (cardiovascular death, non-fatal myocardial infarction related to the target vessel, unplanned ischemia-driven target lesion revascularization) at 1 year

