8.1. Statistical Considerations and Analysis

The statistical analysis plan will be finalized prior to data freeze and will include an in-depth technical description of the statistical analyses described in this section. This section provides a summary of the planned statistical analyses of primary endpoints and key secondary endpoints as listed in section 3.3.

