The TL is the portion of the coronary artery that was in immediate contact with the DCB plus a margin of 5 mm on both ends.

TARGET VESSEL (TV)

The TV is defined as the index coronary artery which was in physical contact with any component (guiding catheter, guide wire, balloon catheter, etc.) of the angioplasty hardware during the initial procedure.

TARGET LESION FAILURE (TLF)

(ARC 2 definition)

Cardiovascular death, target-vessel myocardial infarction, or clinically driven target-lesion revascularization.

TARGET VESSEL FAILURE (TVF)

(ARC 2 definition)

Cardiovascular death, target-vessel myocardial infarction, driven target-vessel revascularization

TARGET LESION REVASCULARIZATION (TLR)

Defined as any repeat percutaneous intervention of the TL or bypass surgery of the target vessel.

Clinically driven revascularizations are those in which the patient has a positive functional study, ischemic ECG changes at rest in a distribution consistent with the target vessel, or ischemic symptoms. Revascularization of a TL with an in-lesion diameter stenosis $\geq 70\%$ (by QCA) in the absence of the above-mentioned ischemic signs or symptoms is also considered clinically driven. In the absence of QCA data for relevant follow-up angiograms, the clinical need for revascularization is adjudicated using the presence or absence of ischemic signs and symptoms.

Non-clinically driven repeat target lesion revascularizations are those in which the patient undergoes a non-emergent revascularization for a diameter stenosis $< 50\%$ (by QCA). Non-emergent repeat target lesion revascularization for a diameter stenosis $< 70\%$ (by QCA) in patients without either a positive functional study or angina are also considered non-clinically driven defined as any repeat revascularization of the target site whether by PCI or bypass surgery.

TARGET VESSEL REVASCULARIZATION (TVR)

Any target vessel revascularization, death, or MI attributed to the target vessel.

TIMI CLASSIFICATION

TIMI 0	No perfusion.
TIMI 1	Penetration with minimal perfusion. Contrast fails to opacify the entire bed distal to the stenosis for the duration of the cine run.
TIMI 2	Partial perfusion. Contrast opacifies the entire coronary bed distal to the stenosis. However, the rate of entry and/or clearance is slower in the

coronary bed distal to the obstruction than in comparable areas not perfused by the dilated vessel.

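### The protocol's body and Appendix A disagree on which revascularizations count in the co-primary TLF, what the target lesion is, and what TVR means

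*Protocol*

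**What the plan says.** **TLF in the body.** Section 3.3.1 gives the clinical co-primary as "cardiovascular death, non-fatal myocardial infarction related to the target vessel, unplanned ischemia-driven target lesion revascularization) at 1 year". Section 3.1 and the synopsis agree. Section 8.3.3, which sets the primary analysis, has the "composite of cardiac death, non-fatal myocardial infarction related to the target vessel, and unplanned ischemia-driven target lesion revascularization": the same TLR term, but cardiac in place of cardiovascular death.

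**TLF in Appendix A.** The entry reads "Cardiovascular death, target-vessel myocardial infarction, or clinically driven target-lesion revascularization". The TLR entry starts from any repeat percutaneous intervention of the target lesion or bypass of the target vessel. It then classes a TLR as clinically driven if there is a positive functional study, ischemic ECG changes at rest, or ischemic symptoms. It adds that revascularization at an in-lesion stenosis of at least 70% by QCA "in the absence of the above-mentioned ischemic signs or symptoms is also considered clinically driven".

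**Target lesion.** Appendix A defines it as the arterial segment in immediate contact with the DCB (drug coated balloon, per Appendix B) plus 5 mm at each end.

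**TVR.** Section 3.3.2 lists target vessel revascularization as secondary endpoint 4. Appendix A defines it as target vessel revascularization, death or MI. Target vessel failure has its own composite entry in the same appendix.

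**The concern.** The trial is single-arm with no hypothesis (section 8.3.1), so the clinical result is one TLF proportion with an exact 95% confidence interval (section 8.3.3). Its meaning rests on the event definition. If two parts of the protocol admit different events, a reader cannot tell what was estimated, and a choice made after the data are seen could look driven by the result.

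The same conflict carries into the first secondary endpoint, the individual components of TLF. The target lesion definition decides which revascularizations are TLRs at all. The TVR entry, if followed, would produce a figure labelled as a revascularization rate that also counts deaths and infarctions.

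**Working it through.** The protocol gives no expected TLF rate, precision target or power, so there is no stated figure to reproduce. The check is a comparison of texts, followed by a sense of scale.

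**1. TLR qualifier.** Take a patient with a repeat PCI of the target lesion, 75% stenosis by QCA, no symptoms, no ECG change and no positive functional study (a constructed case).
- Under 3.3.1 the TLR must be ischemia-driven. On plain words this one is not, so there is no TLF event.
- Under Appendix A the 70% clause makes it clinically driven, so it is a TLF event.

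Ischemia-driven has no definition anywhere in the protocol. The only written rule for classing a TLR is therefore the one that admits a TLR without ischemia.

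**2. Unplanned.** Section 5.6.2 lets the operator leave the lesion unstented at the index procedure and allows a planned staged procedure with a later stent.
- Under 3.3.1 that planned second stage is excluded by the word unplanned.
- Appendix A has no such word. Read literally, the second stage could be a repeat intervention of the target lesion. It would be clinically driven if the patient had symptoms, a positive functional study, or a stenosis of at least 70% by QCA.

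**3. Target lesion.** The device list in section 2 names an everolimus-eluting stent, standard balloons, a cutting balloon, rotational atherectomy and lithotripsy, but no drug coated balloon. The procedure in section 5.6 uses none. A boundary set by contact with that device cannot be applied as written. The stent thrombosis definition in Appendix A already works from the stent with 5 mm on either side.

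**4. TVR.** A target-vessel MI without any repeat procedure is a TVR event under Appendix A, but it is not a revascularization, which is what 3.3.2 lists.

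**5. Scale.** Inputs: target recruitment of 500 (section 8.4); the TLF rates below are assumptions.
- Shift per reclassified patient = 1/n. At n = 500: 1/500 = 0.20 points. The full analysis set (section 8.2) requires follow-up to 12 months and may be smaller; at an assumed 450: 1/450 = 0.22 points.
- Exact (Clopper-Pearson) 95% intervals at n = 500:
  - 25 events (5%): 3.26 to 7.29%, half-width 2.02
  - 40 events (8%): 5.78 to 10.73%, half-width 2.48
  - 50 events (10%): 7.51 to 12.97%, half-width 2.73
  - 75 events (15%): 11.98 to 18.44%, half-width 3.23
- One patient relative to the half-width: 0.20/2.02 = 9.9%; 0.20/2.48 = 8.1%; 0.20/2.73 = 7.3%; 0.20/3.23 = 6.2%.
- Ten patients, as an illustration only: 10/500 = 2.0 points, taking 40 events (8.0%, 5.78 to 10.73%) to 50 events (10.0%, 7.51 to 12.97%). That is close to the 2.48-point half-width.

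**The case against.** **The two TLR terms may be synonyms, and the events committee charter governs.** There is arguably one label in the body and one set of rules in the appendix, rather than two competing rules. Section 14.3 also sends event classification to a charter that is not shown. It stands that the practical effect cannot be judged without the charter. It does not remove the contradiction: the appendix expressly admits revascularization without ischemic signs or symptoms, which the label on its plain words does not.

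**The consequence is limited.** No test, threshold or sample size depends on these definitions. TVR can be rebuilt, because section 5.11 has death, MI and any repeat revascularization adjudicated. Section 11.5 has core laboratories analyse cases with re-PCI in the treated lesion, which helps any reclassification. All of this stands and keeps the point a wording defect that can be repaired.

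**Stronger readings that a reader might infer, and that the documents do not support:**
- *That the death component is an open question.* Section 8.3.3 says cardiac death, but section 8.1 describes section 8 as covering "planned statistical analyses of primary endpoints and key secondary endpoints as listed in section 3.3". The synopsis, 3.1, 3.3.1 and Appendix A all say cardiovascular death. This is stray wording with a clear answer. The MACE label in Figure 2 is the same kind of slip.
- *That QCA thresholds and symptoms contradict each other for a symptomatic TLR below 50% stenosis.* Appendix A says "In the absence of QCA data for relevant follow-up angiograms, the clinical need for revascularization is adjudicated" from ischemic signs and symptoms. This suggests that QCA governs when it is available. It could be clearer, but it is not a shown contradiction.
- *That the TLF estimate will be materially wrong.* Nothing in the protocol tells how many patients fall between the definitions.

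**Conclusion.** The point holds for three definitions that are wrong as written: the TLR qualifier in the co-primary TLF (including the loss of unplanned), the target lesion, and TVR. The first two decide who counts as an event in the clinical co-primary; the third affects one secondary endpoint and is recoverable.

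The size is unknown. Per patient it is small: 0.20 points at n = 500, or roughly 6 to 10% of the interval half-width at assumed rates of 5 to 15%. Only a cluster of reclassified patients, such as the illustrative ten, would move the estimate by an amount comparable to its precision. The MSA co-primary is untouched. The correction should be made, but it does not threaten the design.

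**What to change.** Before data freeze:

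1. Use one TLF definition in the synopsis, 3.1, 3.3.1, 8.3.3, Appendix A and the events committee charter, with one TLR qualifier that is defined in Appendix A. State whether a stenosis of at least 70% by QCA without ischemia counts. Keep or drop unplanned explicitly, and say whether a planned staged procedure is a TLR.
2. Define the target lesion by the segment treated in this trial, for example the stented segment with the existing 5 mm margins. State how a lesion left unstented at the index procedure is handled.
3. Limit TVR to repeat revascularization of the target vessel.
4. Minor corrections: change cardiac to cardiovascular death in 8.3.3, and MACE to TLF in Figure 2.

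The cost is wording in the protocol and charter, plus a re-check of any events adjudicated by then; the protocol does not say whether any have been. No new data are needed and the sample size does not change.

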5.1.2. Patient withdrawal

Subjects may withdraw their consent and discontinue participation in the study at any time for any reason or no reason, without jeopardizing their medical care. If a subject withdraws consent it will be documented on the study exit form, and the reason for withdrawal will be requested.

All data obtained until the date of withdrawal will be kept and entered into the efficacy and safety analysis. If the patient explicitly requests complete deletion of the records, they will be made aware that data pertaining to serious adverse events (SAEs) will be retained. This should be documented by the site. Subjects will not be replaced.

Once the subject is withdrawn, further follow-up of the patients shall proceed according to the hospital standard procedures.

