8.3. Statistical analyses

8.3.1. General considerations

The study design aim is to validate a comprehensive, IVUS guided calcium modification algorithm for moderate to severely calcified coronary lesions and its effects on the primary and secondary outcomes outlined in section 3.3 herein. As such, no statistical hypothesis has been formulated

Proprietary and Confidential - Property of CVRI Dublin, Ireland

in accordance with the single arm, observational design. Descriptive statistics and graphical displays will be used to summarize the study findings and outcomes.

Continuous variables will be summarized by the number of observations, arithmetic mean, standard deviation (SD), median, minimum, maximum and interquartile range unless otherwise stated. For categorial variables, frequency tables will be produced including counts and percentages. Time to event variables will be assessed using Kaplan-Meier curves. There will be no imputation of missing values, unless otherwise described in the statistical analysis plan.

Estimates will be provided with corresponding two-sided 95% Confidence Intervals. No adjustments will be made for multiple testing.

Continuous variables will be reported as mean and standard deviation or median and interquartile range, as appropriate. The distribution of continuous variables will be assessed by the Shapiro-Wilk test. Categorical variables will be reported as counts and percentages and compared by Pearson χ^2 or Fisher exact test, as appropriate. In general, the denominator for the percentage calculation will be based upon the number of non-missing values available, unless otherwise specified.

For time-to-event analysis other than the primary endpoint for the de-novo patients, Kaplan-Meier survival curves as well as confidence intervals based on the log-log transformation will be reported.

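### The 1-year TLF estimate is a crude proportion that ignores event-free follow-up before loss, and the protocol does not settle its denominator

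*Protocol*

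**What the plan says.** Target lesion failure (TLF) at 1 year is one of two co-primary endpoints. Section 8.3.3 puts it on a binary scale ("TLF is a binary endpoint (TLF or no TLF") and states that the primary analysis, on the FAS, "will estimate the proportion of TLF at 1-year with corresponding exact two-sided 95% CI".

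Four other places bear on who enters that proportion:

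- Section 8.2 describes FAS members as having been followed to the end of the study at 12 months.
- Section 5.1.2 (Patient withdrawal): "All data obtained until the date of withdrawal will be kept and entered into the efficacy and safety analysis". Withdrawn subjects are not replaced.
- Section 8.3.1 sets the default for percentages: "In general, the denominator for the percentage calculation will be based upon the number of non-missing values available, unless otherwise specified". It also says: "There will be no imputation of missing values, unless otherwise described in the statistical analysis plan".
- Section 8.5 announces imputation without that condition, then details only partial dates. A missing day becomes the 1st and a missing month becomes January.

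On time-to-event methods, section 8.3.1 first assigns Kaplan-Meier curves to time-to-event variables generally. It then adds a narrower sentence, with log-log intervals: "For time-to-event analysis other than the primary endpoint for the de-novo patients, Kaplan-Meier survival curves as well as confidence intervals". The protocol defines no de-novo group. Section 4.2 requires a native lesion and excludes in-stent restenosis.

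**The concern.** The protocol foresees withdrawal by the patient, withdrawal by the investigator, and loss to follow-up. A binomial proportion needs a 1-year status for every patient it counts, so each incomplete patient must be dropped or coded.

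The information lost is not symmetric. A patient who has TLF and is then lost has a known outcome. A patient who is lost event-free does not, however long the observed event-free time. Dropping the second kind and keeping the first pushes the estimate up even when loss has nothing to do with risk. Coding the second kind as free of TLF pushes it down.

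Two further features make the denominator matter:

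- Read literally, the 12-month condition in section 8.2 removes anyone who died before 12 months. That includes patients whose cardiovascular death is itself the TLF event.
- The 12-month visit may fall 30 days early. A patient last seen event-free at day 335 (365 − 30) has met the schedule but has no observed status at day 365.

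At stake is the headline clinical rate of a single-arm study, which would move with a coding choice the protocol has not made consistently.

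**Working it through.** **Inputs.** From the protocol: N = 500 (section 8.4), the exact CI (8.3.3), and the rules listed above. The protocol gives no expected TLF rate, loss rate or precision target, so the figure of 500 cannot be reproduced. Everything below rests on assumed rates: true TLF p = 10%, loss l = 5% or 10%, and loss spread evenly over the year and unrelated to risk. Let f be the share of the TLF events of patients who are lost that occurs before the loss. If events are spread evenly, f = 0.5. If half are peri-procedural, f = 0.5 + 0.5 × 0.5 = 0.75.

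**Formulas.**

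- Events seen: E = 500(1 − l)p + 500·l·p·f
- Lost event-free: M = 500·l·(1 − p·f)
- Reading A, non-missing denominator with data before withdrawal kept: E / (500 − M)
- Reading B, 12-month completers, taking no account of deaths: 500(1 − l)p / [500(1 − l)] = p
- Reading C, lost patients coded as no TLF: E / 500

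**One case in full** (l = 5%, f = 0.5):

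- E = 47.5 + 1.25 = 48.75 and M = 25 × 0.95 = 23.75.
- A = 48.75 / 476.25 = 10.24%
- C = 48.75 / 500 = 9.75%
- B = 47.5 / 475 = 10.00%

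| Loss | f | A: non-missing | B: completers | C: lost = no TLF |
|---|---|---|---|---|
| 5% | 0.5 | 10.24% | 10.00% | 9.75% |
| 5% | 0.75 | 10.35% | 10.00% | 9.88% |
| 10% | 0.5 | 10.50% | 10.00% | 9.50% |
| 10% | 0.75 | 10.74% | 10.00% | 9.75% |

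**Simulation check.** 3,000 simulated trials of 500 at 5% loss, with half of events peri-procedural, averaged 9.98% by Kaplan-Meier, 10.33% under A, 9.98% under B and 9.85% under C.

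**Wider range.** For TLF of 5 to 15% and loss of 2 to 10%, A overstates by 0.05 to 1.05 points and C understates by 0.03 to 0.75 points.

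**Against sampling error.** The Clopper-Pearson interval at 50/500 is 7.51% to 12.97%, a half-width of (12.97 − 7.51) / 2 = 2.73 points. For TLF of 5 to 15% the half-width runs from 2.0 to 3.2 points.

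**Reading B with deaths.** The 10.00% holds only if patients who die stay in the set. If the 12-month condition also removes k patients whose TLF event was a cardiovascular death, 50/500 becomes (50 − k)/(500 − k), which is below 10% for every k above zero.

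**One data set, three answers** (assumed counts: 50 observed TLF, 2 of them in patients later lost, and 25 patients lost event-free).

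- A: 50/475 = 10.53% (7.91 to 13.64)
- B: 48/473 = 10.15% (7.58 to 13.23)
- C: 50/500 = 10.00% (7.51 to 12.97)
- Upper bound, if all 25 had an event: 75/500 = 15.00% (11.98 to 18.44)

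**The case against.** The strongest reply is that this is a descriptive study with no hypothesis. On that view the coding of lost patients is ordinary SAP detail, section 8.1 leaves technical description to the SAP, and the bias is a fraction of the CI half-width. Section 5.1.4 also works to limit loss, with at least three contact attempts, then the referring physician and an alternative contact. The small size stands. The deferral stands only in part. Section 8.3.4 defers missing-value rules for secondary endpoints, but section 8.3.3 already names the primary estimator. A SAP would also inherit the conflicts between sections 8.2 and 5.1.2 and between 8.3.1 and 8.5.

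A second reply is that time-to-event estimation has its own costs. It relies on dates, and section 8.5 would set a missing month to January, which can place an event before the index procedure. That is fair, and the fix has to cover it.

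A reader might infer three stronger claims that the text does not support:

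- *That TLF will be biased in one known direction, because lost patients count only if they had an event.* The denominator rule is a default with an explicit exception clause. Reading B gives no bias under independent loss when deaths are kept, and reading C reverses the sign.
- *That TLF and its components cannot be reconciled in one report.* Section 8.3.4 summarises secondary endpoints by timepoint, with intervals for frequencies, and never labels the components as time-to-event. A mismatch arises only if they are reported by Kaplan-Meier alone.
- *That a Kaplan-Meier curve for TLF is barred.* The exclusion is tied to an undefined group, and the general sentence in section 8.3.1 carries no exclusion.

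**Conclusion.** The point holds as a cheap improvement. The protocol fixes an estimator that discards event-free follow-up before loss, and it gives conflicting signals on the denominator.

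With true TLF of 10% and independent loss, the non-missing default with withdrawn patients' data kept is high by about 0.2 to 0.35 points at 5% loss and 0.5 to 0.75 at 10%. Coding lost patients as free of TLF is low by up to 0.25 and 0.5 points. Both are below the half-width of about 2.7 points, and no formal decision depends on them. They are nonetheless systematic and avoidable. The TLF rate, the loss rates and the timing of events are assumptions, since the protocol gives none.

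The literal 12-month condition on the FAS deserves attention whichever estimator is used, because it would exclude fatal TLF events from the TLF analysis.

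**What to change.** 1. **Section 8.2:** remove the 12-month follow-up condition from the FAS, so that withdrawn, lost and deceased patients remain. Without this, censoring within the FAS achieves nothing.
2. **Section 8.3.3:** estimate TLF at day 365 as the cumulative incidence from time to first TLF. Censor at last contact, treat non-cardiovascular death as a competing event (Aalen-Johansen), and give a log-log 95% CI. Keep the exact proportion among patients with known 1-year status as a sensitivity analysis.
3. **Section 8.3.1:** delete the exclusion of the primary endpoint for de-novo patients, and use the same estimator for the TLF components.
4. **Sections 8.3.1 and 8.5:** reconcile the two statements on imputation, and add that an imputed event date may not fall before the index procedure.

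The cost is wording in the protocol and SAP. Adverse event onset dates are already collected. The date of last contact should be confirmed as a field on the study exit form. The downside is small: the estimate relies on event and last-contact dates and on non-informative censoring.
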